8.4.2 Reporting other abnormal findings

The other abnormal findings discovered during different clinical assessments (e.g., ECG, spirometry, physical examination, vital signs, body weight) should be evaluated for the clinical significance by the Investigator/designee based on his/her medical judgement. All abnormal clinical significant test results or clinical examination findings can, at the discretion of the Investigator, be reported as AEs and handled according to the directions from section 8.2.

8.5 Reporting and Follow-Up of Pregnancies

8.5.1 Period of Collection and Follow-up

Pregnancies detected between the time of signature of the ICF and first exposure to the IP will be considered a reason for screen failure. No pregnancy form will be filled in that case, however the diagnosed pregnancy must be captured in the screen failure page of the CRF.

Any pregnancy that was potentially associated with exposure to the IP, including pregnancies spontaneously reported to the Investigator after the EOS must be reported by the Investigator and followed-up until the pregnancy outcome is reached (e.g. normal delivery, spontaneous abortion, voluntary termination) and also until 8 weeks after delivery. Potential association with the exposure to the IP is defined as exposure to IP during or after the calculated conception date.

Any pregnancy complication, adverse pregnancy outcome or maternal complications will be recorded as an AE accordingly.

8.5.2 Reporting of Pregnancies

A dedicated pregnancy form will be used to report reportable cases of pregnancy.

The procedure to report a pregnancy and provide any additional/follow-up information to UBC Pharmacovigilance is the same and performed within the same timelines as the one described for an SAE (section 8.3).

The Investigator is responsible for informing the corresponding IEC of the any pregnancy case that was reported during the study, as determined by local regulations.

Confidentiality Statement

Data and information contained in this document are considered to constitute trade secrets and confidential commercial information, and the legal protections provided to such trade secrets and confidential information are hereby claimed under the provisions of applicable law. No part of this document may be publicly disclosed without the written consent of Philip Morris Products S.A.

8.6 Adverse Events Leading to Discontinuation

Subjects who are discontinued from the study because of an AE will undergo the early termination procedures (section 9.6), as soon as practical after discontinuation and will enter the 7-day Safety Follow-Up Period. In general, AEs will be followed-up until resolved, stabilized (i.e., no worsening of the event), or a plausible explanation has been found and until the end of the study.

Any AEs or SAEs that are ongoing at the end of the Safety Follow-Up Period will be managed as described in section 8.2.6.

8.7 Investigational Product Malfunction and Misuse

Any occurrence of P3P malfunction or misuse (use not in accordance with its instruction) by a subject will be documented by the Investigator using a Product Issue Log. Information regarding product malfunction or misuse should be actively collected during the study visits.

Furthermore, any malfunction or misuse of P3P that leads to an AE/SAE will follow the same processes as described above.

Confidentiality Statement

Data and information contained in this document are considered to constitute trade secrets and confidential commercial information, and the legal protections provided to such trade secrets and confidential information are hereby claimed under the provisions of applicable law. No part of this document may be publicly disclosed without the written consent of Philip Morris Products S.A.

9 STUDY ACTIVITIES

A detailed schedule of all study activities and assessments is provided in Appendix A. Measurements not conducted at the exact time point indicated, but conducted within the given time window (if applicable) do not constitute a protocol deviation but an accepted variability for the given time point.

In general, if no start time for the procedure is provided, then the procedure can be performed at any time during the day.

9.1 Screening Visit

The Screening Visit will be performed within 3 weeks prior to Admission. First, the ICF along with study information should be given to the subject. Prior to being asked to sign the consent form, subjects will be given time to review the study information and ask any questions. When/if the ICF is signed, dated and timed, the other screening procedures can be performed in the order deemed most practical. While it is recommended to complete as many screening procedures as possible in one day, it is permissible to complete those over more than one day. Smoking is allowed at the Screening Visit at the discretion of the investigational site.

Screening activities are listed in Table 7.

Table 7 Time Schedule – Screening Visit

Time	Blood Sample	Procedures	Additional Information
Start of Procedure			
Prior to any other procedure		Collection of informed consent Information on risks of smoking, smoking cessation advice and product debrief Smoking history/habits questionnaire FTND questionnaire Demographic data Medical history/ concomitant disease Prior (within 4 weeks prior to Screening) and concomitant medication	

Confidentiality Statement

Data and information contained in this document are considered to constitute trade secrets and confidential commercial information, and the legal protections provided to such trade secrets and confidential information are hereby claimed under the provisions of applicable law. No part of this document may be publicly disclosed without the written consent of Philip Morris Products S.A.

Time	Blood Sample	Procedures	Additional Information
Start of Procedure			
		Physical examination	
		Body height, weight and calculated BMI	
		Vital signs (blood pressure, pulse rate, respiratory rate)	At least 5 min in supine position prior to measurement. At least 15 minutes smoking abstinence prior to measurement.
		ECG	After resting for at least 10 min in supine position prior to recording
		Spirometry	Has to be done at least 1 hour after smoking. After resting in sitting position for at least 15 minutes prior to testing.
	✓	Clinical laboratory parameters (hematology, clinical chemistry)	
		Collection of spot urine for: 
 - Urine analysis safety panel - Urine drug screen - Urine cotinine screen - Urine pregnancy test (all female subjects) 	
	✓	Serology	HIV 1/2, Hepatitis B and C
		Alcohol breath test	
During the visit		Review of inclusion/exclusion criteria based on all relevant assessments	Includes readiness to comply to study procedures, including smoking interruptions; intention to quit smoking in the next 2 months
		P3P demonstration	Without product use
During the visit		AE/SAE recording	If the Screening Visit is performed on two separate days the AE/SAE questions will be asked again.

Abbreviations: AE = Adverse event; BMI = Body mass index; ECG = Electrocardiogram; FTND = Fagerström Test for Nicotine Dependence; HIV = Human immunodeficiency virus; SAE = Serious adverse event.

Confidentiality Statement

Data and information contained in this document are considered to constitute trade secrets and confidential commercial information, and the legal protections provided to such trade secrets and confidential information are hereby claimed under the provisions of applicable law. No part of this document may be publicly disclosed without the written consent of Philip Morris Products S.A.

9.2 Admission Visit

The assessments performed at Admission are listed in Table 8.

Table 8 Time Schedule – Admission Visit

Time	Blood Sample	Procedures	Additional Information
Start of Procedure			
Before enrollment		Information on risks of smoking, smoking cessation advice and product debrief Concomitant medication Physical examination Vital signs (blood pressure, pulse rate, respiratory rate)	At least 5 min in supine position prior to measurement. At least 15 minutes smoking abstinence prior to measurement.
		ECG	After resting for at least 10 min in supine position prior to recording.
		Urine drug screen Urine pregnancy test (all female subjects) Alcohol breath test	
		Review of Inclusion criteria 6 and 8 and exclusion criteria 7, 9, 10, 15, 16 and 17	
		Enrollment	
	✓	Clinical laboratory parameters (hematology, clinical chemistry)	After at least 6 hours of fasting.
		Urine analysis safety panel	
		Cough assessment	VAS, Likert and open question
After enrollment		P3P product test by subject	Using up to three P3P 3 products
After product test		Collection of used products	
During the visit		AE/SAE recording	
During the visit		Product events malfunctions/misuse	

Abbreviations: AE = Adverse event; ECG = Electrocardiogram; SAE = Serious adverse event; VAS = Visual analogue scale

Confidentiality Statement

Data and information contained in this document are considered to constitute trade secrets and confidential commercial information, and the legal protections provided to such trade secrets and confidential information are hereby claimed under the provisions of applicable law. No part of this document may be publicly disclosed without the written consent of Philip Morris Products S.A.

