4.4 Study Duration

The entire study per subject will last 14 to 34 days. This will include a Screening period of up to 3 weeks prior to Admission (Day -22 to Day -2), 6 days of confinement (Day -1 to time of Discharge on Day 5), and a 7-days passive Safety Follow-Up (from time of Discharge at Day 5 until Day 12). The end of the study (EOS) for a subject is defined as either the Discharge at Day 5, or the date of early termination of the subject, plus the 7 days for the Safety Follow-Up Period. The end of the whole study corresponds to the individual EOS of the last subject.

Confidentiality Statement

Data and information contained in this document are considered to constitute trade secrets and confidential commercial information, and the legal protections provided to such trade secrets and confidential information are hereby claimed under the provisions of applicable law. No part of this document may be publicly disclosed without the written consent of Philip Morris Products S.A.

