5.1.1 Inclusion Criteria

Subjects must meet all of the following inclusion criteria to be enrolled into the study:

Inclusion Criteria	Rationale	Screening Visit	Admission Visit
1. Subject has signed the ICF and is able to understand the information provided in the ICF.	Administrative	X	
2. Smoking male or female aged between 21 and 65 years old.	Safety	X	
3. Subject is White. ^a	Effect	X	
4. Subject has been a smoker for at least the last 3 years prior to the Screening Visit.	Effect	X	
5. Has smoked \geq 10 commercially available cigarettes per day for 4 weeks prior to Screening Visit. Smoking status will be verified based on a urinary cotinine test (cotinine \geq 200 ng/mL).	Effect	X	
6. Subject does not plan to quit smoking within 2 months after Screening Visit.	Safety	X	X
7. Smoking, healthy subject as judged by the Investigator or designee based on available assessments from the Screening period (e.g., safety laboratory, spirometry, vital signs, physical examination, ECG and medical history).	Safety	X	
8. Availability for the entire study period and willingness to comply with study	Effect	X	X

Confidentiality Statement

Data and information contained in this document are considered to constitute trade secrets and confidential commercial information, and the legal protections provided to such trade secrets and confidential information are hereby claimed under the provisions of applicable law. No part of this document may be publicly disclosed without the written consent of Philip Morris Products S.A.

Inclusion Criteria	Rationale	Screening Visit	Admission Visit
procedures, including smoking interruptions.			
9. Ready to accept using the P3P product.	Effect	X	

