5.1.2 Exclusion Criteria

Subjects who meet any of the following exclusion criteria must not be enrolled into the study:

Exclusion Criteria	Rationale	Screening Visit	Admission Visit
1. As per the Investigator's judgment, the subject cannot participate in the study for any reason other than medical (e.g., psychological and/or social reason).	Safety	X	
2. Subject is legally incompetent, or physically or mentally incapable of giving consent (e.g., emergency situation, under guardianship, prisoners, or subjects who are involuntarily incarcerated).	Administrative	X	
3. Subject has a clinically relevant disease which requires medication (including but not limited to gastrointestinal, renal, hepatic, neurological, hematological, endocrine, oncological, urological, immunological, pulmonary, and cardiovascular disease) or any other clinically significant medical condition (including safety laboratory), which as per the judgment of the Investigator would jeopardize the safety of the subject.	Safety	X	

Confidentiality Statement

Data and information contained in this document are considered to constitute trade secrets and confidential commercial information, and the legal protections provided to such trade secrets and confidential information are hereby claimed under the provisions of applicable law. No part of this document may be publicly disclosed without the written consent of Philip Morris Products S.A.

Exclusion Criteria	Rationale	Screening Visit	Admission Visit
4. As per the Investigator's judgment, the subject has medical conditions which require or will require in the course of the study, a medical intervention (e.g., start of treatment, surgery, hospitalization) which may interfere with the study participation and/or study results.	Effect	X	
5. Subject has donated or received whole blood or blood products within 3 months prior to Screening Visit.	Safety	X	
6. Subject has a BMI < 18.5 kg/m ² or > 32.0 kg/m ² .	Safety	X	
7. Subject has received medication within 14 days or within 5 half-lives of the drug prior to Admission (whichever is longer) which has an impact on CYP2A6 activity.	Effect		X
8. Subject has a positive serology test for HIV 1/2, Hepatitis B, or Hepatitis C.	Safety	X	
9. Subject has a positive alcohol breath test and/or a history of alcohol abuse that could interfere with the subject's participation in study.	Administrative	X	X
10. Subject has a positive urine drug test.	Administrative	X	X

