7.7.1 Blood Samples

Blood samples will be drawn by qualified and trained site personnel. Since the test for nicotine concentration is highly sensitive, precautions should be taken during blood sampling and processing to prevent the contamination of samples with environmental nicotine. Subjects should be in a seated position during blood collection.

In total, around 464 mL will be drawn for this study including samples for determination of nicotine concentrations, CYP2A6 activity and safety. This calculation is based on an individual volume of each sample of 5 mL for nicotine PK (of which 4 mL is needed for nicotine dosing and 1 mL for cannula rinsing of saline solution as per site's SOPs), 4 mL for CYP2A6 analysis and 12.5 mL for safety laboratory assessments. The total volume of blood drawn will not exceed the levels for a standard blood donation.

More details on the procedures for collection, labeling, handling and shipment of samples are described in a separate SHM.

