Study Day	Day -22 to -2 Screening	Day -1 Admission	Day 1	Day 2	Day 3	Day 4	Day 5 Discharge ^a	Day 5 to 12 Safety Follow-Up ^o
Blood sample collection for plasma nicotine ^k			•	•	•	•	•	
VAS-craving ^l			•	•	•	•		
Adapted mCEQ ^m			•	•	•	•		
Sensory Questionnaire ^m			•	•	•	•		
Cough assessment ⁿ		•		•	•	•	•	
AE/SAE recording ^o	•	•	•	•	•	•	•	•
Product events Malfunctions/Misuse		•	•	•	•	•		
Support during periods of smoking abstinence (as required)			•	•	•	•	•	
Weighing of P3P products ^p			•	•	•	•		

Abbreviations: Adapted mCEQ = adapted version of the modified Cigarette Evaluation Questionnaire; AE = Adverse event; BMI = Body mass index; ECG = Electrocardiogram; FTND = Fagerström Test for Nicotine Dependence (revised version); HPT = Human puffing topography; SAE = Serious adverse event; SQ = Sensory questionnaire; VAS= Visual Analog Scale.

- a. Prior to enrollment at Admission the following inclusion and exclusion criteria will be re-checked: **Inclusion Criteria:** Subject is not planning to quit smoking within 2 months, Subject is available during the study period and ready to comply with study procedures. **Exclusion criteria:** Subject has a positive alcohol test and/or the subject has a history of alcohol abuse that could interfere with the subject's participation in study, subject has a positive urine drug screen, subject uses estrogen containing medication, female subject who is pregnant or breast-feeding, female subject of childbearing potential who does not agree to use effective contraception. The following eligibility criteria will only be checked at Admission: subjects will not be included if they have received medication within 14 days or within 5 half-lives of the drug prior to Admission (whichever is longer) which has an impact on CYP2A6 activity.
- b. Sex, date of birth, race.
- c. All medication taken within 4 weeks prior to the Screening Visit will be documented. Prior medication which has an impact on CYP2A6 activity taken within 14 days or within 5 half-lives of the drug (whichever is longer) prior to Day -1 is an exclusion criteria.
- d. Systolic and diastolic blood pressure, pulse rate and respiratory rate. Assessed in the morning within 60 minutes prior to fixed puffing regimen and 60 minutes \pm 10 minutes after each product use period (fixed puffing regimen and *ad libitum* use).
- e. On Days 1 to 4 ECG, will be performed after fixed puffing regimen and after the *ad libitum* use period.

Confidentiality Statement

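### Exclusion 5 stops counting blood donations at the Screening Visit and is not reviewed at Admission, so a donation in the gap of up to 21 days goes unchecked

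*Protocol*

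**What the plan says.** The time between the two checks is set in protocol section 4.4: "This will include a Screening period of up to 3 weeks prior to Admission (Day -22 to Day -2". Enrolment and the first product use both take place at Admission on Day -1.

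Table 8 in section 9.2 places a physical examination, vital signs and an ECG above the Enrollment row. The eligibility item in the same block reads: "Review of Inclusion criteria 6 and 8 and exclusion criteria 7, 9, 10, 15, 16 and 17". Appendix A, footnote a, gives the same eight criteria in words, introduced by "Prior to enrollment at Admission the following inclusion and exclusion criteria will be re-checked". The Admission column of section 5.1 and the copied table in SAP 6.2 agree.

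The criteria outside that list that matter here are all marked for Screening only:

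- Exclusion 5, rationale Safety: "Subject has donated or received whole blood or blood products within 3 months prior to Screening Visit".
- Inclusion 7, rationale Safety: "Smoking, healthy subject as judged by the Investigator or designee based on available assessments from the Screening period".
- Exclusion 3, rationale Safety, which begins "3. Subject has a clinically relevant disease which requires medication".
- Exclusion 4, rationale Effect: "the subject has medical conditions which require or will require in the course of the study, a medical intervention".

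On blood volume, section 7.7.1 gives a total of about 464 mL and adds: "The total volume of blood drawn will not exceed the levels for a standard blood donation". Sections 2.3.2 and 2.3.3 use the same comparison when describing risk and its mitigation.

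**The concern.** Exclusion 5 is a safety criterion about recent blood loss, yet its window closes at Screening while the study's own sampling mostly starts after Admission. A donation in between falls outside the window as worded. The Admission schedule records concomitant medication and adverse events, but a donation is neither, and no listed item asks about it.

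The protocol justifies the sampling load by setting it against one donation. Section 2.3.2 names weakness, dizziness and anemia as risks of the total volume taken over a period of time. For someone who has just donated, the relevant total is the donation plus the study blood.

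The protocol already has the wording it needs. Exclusion 7 counts back from Admission and is checked there. Exclusions 9 and 10, labelled Administrative, are also re-checked at Admission, whereas exclusion 5 is not.

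A second, smaller matter is that the clinical assessments done before enrolment at Admission have no counterpart among the criteria reviewed there, and inclusion 7 is worded on Screening-period data only.

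**Working it through.** **1. Length of the gap.** The earliest Screening day is -22 and Admission is Day -1, which gives 21 days. Section 4.4 counts Day -1 to Day 5 as 6 days of confinement, so there is no Day 0. From Day -22 to Day 5 the elapsed time is 21 + 1 + 4 = 26 days.

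**2. Which criteria are reviewed at Admission.** The lists in section 5.1 (Admission column) and Table 8 are the same: inclusion 6 and 8; exclusion 7, 9, 10, 15, 16 and 17. None of inclusion 7 or exclusions 3, 4 and 5 is among them. The sources do not contradict one another; the gap lies in the design.

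**3. The plan's blood volume.** Inputs are from sections 7.5.1, 7.6.1 and 7.7.1.

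- Nicotine samples: (10 + 8) × 4 days + 5 on Day 5 = 77; 77 × 5 mL = 385 mL.
- CYP2A6 sample: 4 mL.
- Safety panels at Screening, Admission and Days 2 to 5: 6 × 12.5 mL = 75 mL.
- Total: 385 + 4 + 75 = 464 mL, which reproduces the stated figure.

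**4. Combined loss with a donation in the gap.** The documents give no donation volume, so 400 to 500 mL is an assumption.

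- With all study blood: 400 + 464 = 864 mL; 500 + 464 = 964 mL.
- Counting only study blood drawn after the Screening panel (464 − 12.5 = 451.5 mL): 851.5 to 951.5 mL.

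**5. Whether re-listing alone would help.** Adding exclusion 5 to Table 8 without changing its text would not catch the case, because a donation after Screening is still outside a window that ends at Screening. The reference date has to move as well.

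**6. The Admission assessments.** None of the eight listed criteria draws on the examination, vital signs or ECG. Against that:

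- The protocol's definition of Enrollment requires all applicable criteria to be assessed and met.
- Section 5.4 makes anyone who fails the entry criteria between consent and enrolment at Admission a screen failure.
- Section 5.2 requires discontinuation for a condition that the Investigator considers no longer justifies participation. Table 8 puts Enrollment before the product test, so this can act before first use.

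**The case against.** The strongest reply is that the visit columns show when a check is scheduled, not when a criterion is in force. Exclusion 3 is in the present tense and undated, exclusion 4 looks forward, and section 5.4 covers the whole period from consent to enrolment. A reader might infer from Table 8 that a subject with a new clinically significant ECG or examination finding would be enrolled. The documents do not support that, for the reasons in step 6 above.

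Nor do they support the inference that the Admission assessments serve no purpose. Section 7.4.8.1 has every ECG classified for clinical significance, section 8.4.2 has abnormal findings evaluated, and the SAP's ECG section takes Day -1 as baseline.

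A reader might extend the point to exclusion 13 (other clinical studies). Its first sentence refers to the Screening Visit, but its second runs the interval to the first day of the present study, so the text does not establish the same gap.

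On blood, three replies carry weight. First, the statement in section 7.7.1 concerns blood drawn for the study and stays true whatever a subject donates elsewhere. Second, a fixed total of at least 928 mL could be inferred by reading that comparison as making a donation at least 464 mL (464 + 464 = 928), but no volume is stated. Third, haematology at Admission and on Days 2 to 5 would monitor a fall in haemoglobin, although Table 8 lists the Admission sample after Enrollment. In addition, the consent form is not available here and might tell subjects not to donate.

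None of this alters the end date of the exclusion 5 window or adds a question at Admission.

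**Conclusion.** The exclusion 5 gap stands. For up to 21 days before first exposure, a blood donation breaches no criterion in the protocol or SAP, and no scheduled Admission item would bring it to light. If it happened, the combined loss would be about 864 to 964 mL within about 26 days, on the assumption of a 400 to 500 mL donation. The documents give no basis for saying how often this would occur.

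The part about inclusion 7 and exclusions 3 and 4 stands only as a need for alignment: the protocol collects the relevant data before enrolment and has general rules that let the Investigator act on them, but the Admission list does not connect the two. It is not a route to enrolling an unfit subject.

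The listed sources agree with one another, and no sample-size or error-rate figure is involved. Severity: minor.

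**What to change.** - **Exclusion 5.** Make the look-back reach Admission, as exclusion 7 already does, and mark the criterion for the Admission review. Change the synopsis, section 5.1.2, Table 8, Appendix A footnote a and the copied table in SAP 6.2 together. Add one interview question at Admission on donation or receipt of blood since Screening.
- **Inclusion 7 and exclusions 3 and 4.** Reconcile section 5.1, Table 8, Appendix A footnote a and SAP 6.2 with the definition of Enrollment and section 5.4, so that the examination, vital signs and ECG already done before enrolment inform these criteria. Inclusion 7 should no longer rest on Screening-period data alone.

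The cost is a wording amendment, which section 1.1 requires to go to the ethics committee, one extra question per subject, and possibly a few more screen failures at Admission. No new procedure is needed, no clinical threshold is introduced, and the 464 mL figure does not change.
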